6.1 Statistical Methods

A two-way rmANOVA will test for significant main effects and interactions between time (Pre versus Post) and experimental session (perturbations versus normal walking). Significance will be defined for each main effect using an alpha level of 0.05.

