	
 1. Current lower extremity injury or fracture 2. Taking medication that causes dizziness 3. Have a leg prosthesis 4. Prisoners 5. Individuals lacking the capacity to provide informed consent

Number of Subjects	Up to 20
Study Duration	
Each subject will participate in two sessions, each lasting up to three (3) hours and separated by at least one week.
 
The entire study is expected to last two years (approximately one year for data collection and another one year for data analysis)

Study Phases	
Screening	(1) Screening : We will use an initial telephone screening (attached) to evaluate basic study eligibility. Subjects that meet inclusion/exclusion criteria following phone screening will be invited to participate in the study.
Study Treatment	
Follow-Up	(2) Balance training : Subjects that provide written informed consent will participate in the cross-over design that includes one control session and one session of perturbation training, separated by at least one week.
Efficacy Evaluations	
Primary outcome measures:
 
(1) Change in Postural Sway
 
(2) Change in kinematic (step width) variability
 
(3) Change in foot placement targeting accuracy
 
Secondary outcome measures:
 
(1) Change in Cognitive-motor Interference Accuracy
 
(2) Change in Cognitive-motor Interference Response Time After 10 Min of Walking
 
(3) Change in Margin of Stability Variability After 10 Min of Walking

Statistical Analysis Plan	A one-way, repeated-measures analysis of variance will test for effects of time on dependent variables collected from each session. Significance will be defined using an alpha level of 0.05.
DATA AND SAFETY MONITORING PLAN	This study does not meet the criteria for an independent DSMP. The PI ([name]) will oversee all conduct to ensure the safety of all participants and the integrity of the data. At least one research staff member will be monitoring the subjects' movement patterns during the data collection. If the subject experiences any discomfort, the data collection will be stopped immediately. If any member of the research team encounters unanticipated problems (including but not limited to adverse events), we will make necessary adjustments to the protocol and, where appropriate, report these events to University administrative personnel.

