2.1 Primary Objective

Quantify the time-dependent changes in metrics of walking balance in older adults after walking with optical flow perturbations.

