2.2 Secondary Objective

Contrast effects of walking with optical flow perturbations to those of normal treadmill walking.

3 INVESTIGATIONAL PLAN (brief overview)

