3.1 Study Design

(Session A: Normal walking, Session B: Continuous optical flow perturbations). In a randomized cross-over designed (assigned at enrollment using a random number generator), subjects will walk normally (session A) and be exposed to continuous side-to-side motions of the virtual hallway (Session B). These walking trials will last up to 20 min and will be separated by at least one week.

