3.3 Study Population

Inclusion Criteria:

1. Subjects Age 65+ years
2. Be able to walk without an assistive aid (i.e., walker, cane)
3. Have the full capacity to provide informed consent

Exclusion Criteria:

1. Current lower extremity injury or fracture
2. Taking medication that causes dizziness
3. Have a leg prosthesis
4. Prisoners
5. Individuals lacking the capacity to provide informed consent

4 STUDY PROCEDURES (what will be done)

Subjects will be comfortably fit with a safety harness and instructed on all safety procedures. Subjects will then walk at their preferred speed on a force-sensing treadmill for 5 min to acclimate to the equipment and allow their movement patterns to stabilize.

Subjects will then complete a block protocol design with pre and post measurements separated by up to 20 min of normal treadmill walking (Session A) or in the presence of optical flow perturbations (Session B). Pre and post measurements will include baseline measurements during normal walking and:

- 1) Foot placement targeting task. Subjects will be exposed to a series of footprint targets intermittently projected onto the treadmill belt. Subjects will be asked to direct their feet to the target with their next step as accurately as possible.
- 2) Auditory 'Stroop' task. While wearing headphones with a microphone, subjects will hear the words high and low in pitches that are either high or low and asked to verbally identify the pitch of those words as quickly as possible.

Subject Completion/ Withdrawal procedures

If subjects are unable to complete the protocol or suffer a musculoskeletal injury before or during the time period when they are involved in the study, they will be withdrawn from the study.

5 STUDY EVALUATIONS AND MEASUREMENTS (how measurements will be made)

3D motion capture and an instrumented treadmill will record the position and orientation of body segments and joints and ground reaction forces. Using custom software, we will compute the mean and standard deviation of step width variability, postural sway variability, and margin of stability variability. The outcome measure from the foot placement targeting task will be foot placement accuracy. The outcome measures from the auditory Stroop task will be cognitive-motor interference accuracy and response time. Efficacy measurements will be made using the change in each outcome measure after walking normally or with optical flow perturbations.

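### Optional improvement: block the session order in section 3.1 and, with it, add an order term to the between-session test in 6.1 for foot placement targeting and the auditory Stroop

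*Combined protocol and SAP*

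**What the plan says.** - Section 3.1 describes the allocation: "In a randomized cross-over designed (assigned at enrollment using a random number generator". It gives no blocking or ratio. Sessions are at least one week apart.
- Section 6.1 gives the analysis: "A two-way rmANOVA will test for significant main effects and interactions between time (Pre versus Post) and experimental session (perturbations versus normal walking". Alpha is 0.05. The synopsis has a one-way repeated-measures analysis of time within each session. Neither has an order, sequence or visit term.
- The session comparison is the secondary objective (2.2): "Contrast effects of walking with optical flow perturbations to those of normal treadmill walking". The primary objective (2.1) is a within-session question: "Quantify the time-dependent changes in metrics of walking balance in older adults after walking with optical flow perturbations".
- Section 5 defines the estimand as a change: "Efficacy measurements will be made using the change in each outcome measure after walking normally or with optical flow perturbations".
- Section 4 has subjects "walk at their preferred speed on a force-sensing treadmill for 5 min to acclimate to the equipment and allow their movement patterns to stabilize". It continues, "Pre and post measurements will include baseline measurements during normal walking and" then lists the foot placement targeting task and the auditory Stroop task. It describes no practice on either task.
- The synopsis lists "Change in foot placement targeting accuracy" as one of three primary outcomes. The Stroop supplies two of the three secondary outcomes.
- Section 3.2 caps recruitment at 20.

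**The concern.** In a two-session crossover the time x session interaction is the same as a paired test on each subject's session difference in change. If subjects simply perform better or worse at visit 2, equally before and after walking, that shift cancels. If the pre-to-post change itself differs between visits, it does not cancel.

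Such a difference is plausible for the two task-based measures. The visit 1 pre measurement may be a subject's first attempt at the task, so early practice could enlarge the visit 1 change relative to the visit 2 change. The randomised order is known for every subject and could absorb this, but the model in 6.1 does not use it. What is at stake is some precision in the only randomised comparison, with at most 20 subjects. Nothing is claimed here for postural sway, step width variability or margin of stability, or for the primary objective.

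**Working it through.** **The plan's own figure.** Section 6 gives 14 per group for 90% power, older 1.38 (SD 0.20) against young 1.20 (SD 0.10). Pooled SD = sqrt((0.20² + 0.10²)/2) = 0.158, so d = 0.18/0.158 = 1.14. With a t test this reproduces as one-sided 0.05 (90.1% at 14 per group); two-sided, 14 gives 82.6% and 18 are needed. It compares two age groups and does not size the within-subject session contrast. Below, n=14 is only a smaller illustration beside n=20.

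**Model.** Let D be a subject's change in the perturbation session minus the change in the normal session:

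D = tau + pi·s + e, SD(e) = 1, s = +1 if perturbation comes first and -1 otherwise.

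Here pi is the visit 1 minus visit 2 difference in change, in SDs of the within-subject session difference in change. The documents give no value, so 0 to 0.5 is assumed. The session effect tau is set so that the paired test has 90% power at pi = 0, two-sided 0.05: 0.7645 (n=20) and 0.9382 (n=14).

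- Without the order term: the estimate has mean tau + pi(n1 - n2)/n, and the variance estimate has mean 1 + pi²[n - (n1 - n2)²/n]/(n - 1), on n - 1 df.
- With it: the estimate has mean tau and SE = sqrt((1/n1 + 1/n2)/4), on n - 2 df.

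Example, n=20 at 10:10 and pi = 0.5: without the term the mean variance estimate is 1 + 0.25 × 20/19 = 1.263 instead of 1.

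**Equal orders, power**

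| n | pi=0 | 0.1 | 0.25 | 0.5 | with term | break-even |
|---|---|---|---|---|---|---|
| 20 | 90.0% | 89.8% | 88.8% | 84.8% | 89.8% | 0.10 SD |
| 14 | 90.0% | 89.8% | 88.7% | 84.5% | 89.6% | 0.14 SD |

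At n=20 the mean confidence-interval half-width without and with the term is 0.4769 against 0.4633 at 0.25 SD (2.9% wider) and 0.5194 against 0.4633 at 0.5 SD (12.1% wider). Type I error without the term is 4.4% and 2.9%, so the 6.1 test is conservative here.

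**Unequal orders, n=20, no term.** At pi = 0.5 the shift is 0.5 × 4/20 = 0.10 SD at 12:8 and 0.5 × 8/20 = 0.20 SD at 14:6, with conditional type I error 4.5% and 9.7%. Power at 12:8 is 92.7% or 73.2% depending on the sign of pi, against 88.6% with the term. Under unrestricted assignment (an assumption) a split of 12:8 or worse has probability 50%, and 14:6 or worse 11.5%. Averaged over splits, type I error is 5.0%.

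**Unrestricted assignment, average power**

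| n | no term: pi=0 | 0.25 | 0.5 | with term | break-even |
|---|---|---|---|---|---|
| 20 | 90.0% | 88.2% | 82.7% | 88.1% | 0.26 SD |
| 14 | 90.0% | 88.2% | 82.7% | 86.9% | 0.33 SD |

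**Withdrawals from a blocked 20**, at random (an assumption; no rate is given), tau reset to 90% for the completers

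| lost | with term | cost at pi=0 | break-even | gain at 0.25 SD |
|---|---|---|---|---|
| 2 | 89.6% | 0.4 points | 0.14 SD | 0.9 points |
| 4 | 89.3% | 0.7 points | 0.18 SD | 0.7 points |
| 6 | 88.9% | 1.1 points | 0.22 SD | 0.3 points |

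**Carryover.** If perturbation-first subjects carry 0.5 SD into their second-session change, half the subjects at 10:10 are affected. The bias is 0.5 × 0.5 = 0.25 SD in size, with or without the term.

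**The case against.** The strongest reply is that 6.1 needs no change. Its test is unbiased over randomisation, and conservative when orders are equal and a visit effect is present. The documents give no SD, correlation or practice effect for either task, and a brief procedures section that is silent on task practice does not show that there was none. The gain at 0.25 SD is about one power point. With order unblocked, as 3.1 leaves open, the term would on average lose power over much of the assumed range. All of this stands. It makes the point an optional refinement and makes blocking its first half.

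Three stronger readings are tempting, and the documents support none of them:

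- A reader might infer that omitting order makes the session test biased or anti-conservative. The 9.7% figure needs both a 14:6 split and a 0.5 SD visit effect; the rate over randomisation is 5.0%.
- A reader might take 0.1 SD as the point where a worthwhile gain begins. It is the break-even at exactly 10:10, and it rises with smaller numbers or withdrawals.
- A reader might conclude that 6.1 alone should be amended. Without blocking, the term costs 1.9 points (n=20) or 3.1 points (n=14) on average when there is no visit effect.

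What remains is the asymmetry. With blocking and equal orders at n=20, including the term risks 0.2 points, while omitting it risks about 5 points if the visit effect is 0.5 SD.

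**Conclusion.** This is a cheap improvement that the sponsor could make, not an error in the plan. Order is randomised with no stated blocking, and the between-session test does not use it. Blocking and the order term together pay if the visit effect on the change exceeds 0.10 SD (n=20, 10:10) or 0.14 SD (n=14, 7:7), or 0.14 to 0.22 SD if 2 to 6 of a blocked 20 withdraw. The benefit becomes material only towards 0.5 SD. These sizes rest on an assumed visit effect, a session effect set at 90% power, normal errors and random withdrawal. The conclusion covers foot placement targeting and the auditory Stroop in the session contrast only. The order term should not be presented as protection against carryover.

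**What to change.** Make both changes together, for subjects not yet assigned an order.

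1. Section 3.1: *Session order is generated in permuted blocks of randomly mixed sizes 2 and 4.*
2. Section 6.1, between-session contrast only: *Each subject's session difference in change (perturbation minus normal) is regressed on session order coded +1/-1, and the intercept is tested at two-sided 0.05.*

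Leave the pre-to-post test within the perturbation session, which serves the primary objective, as it is. If order will not be blocked, leave the term out by default and state the break-even that applies then.

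The cost is wording, a blocked list and one degree of freedom: with equal orders and no visit effect, 0.2 power points at n=20 (90.0% to 89.8%) or 0.4 at n=14 (90.0% to 89.6%), and somewhat more after withdrawals. No new data are needed. Small blocks make some assignments predictable to staff; mixing the sizes reduces this but does not remove it.

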Study Rationale	
One third of adults age 65 and older fall annually with 20-30% of falls resulting in serious injuries. In 2009 alone, falls in older adults resulted in nearly 2.2 million emergency room visits. In 2000, direct medical cost of non-fatal falls in adults over age 65 was \$19 billion, and in 2007 that cost was projected to increase to \$54.9 billion/year by 2020. However, despite considerable efforts, falls rates over this time have been highly resistant to change. Thus, there is a critical need for more effective diagnostic efforts to identify older adults at risk of falls and rehabilitative efforts to successfully mitigate that risk once identified. Consistent with studies on the postural control of standing, our recent findings suggest that older adults prioritize visual feedback to control balance in walking.
 
Accordingly, older adults are more susceptible than young adults to optical flow perturbations applied in the safety of virtual reality (VR). These perturbations elicit the visual perception of walking instability, and provide the opportunity to practice walking balance corrections in a controlled environment. The purpose of this proof of concept study is to investigate the propensity for time-dependent tuning of walking balance control and the presence of aftereffects in older adults following a single session of optical flow perturbation training.

Study Objective(s)	To investigate the propensity for time-dependent tuning of walking balance control and the presence of aftereffects in older adults following a single session of optical flow perturbation training.
Test Article(s) (If Applicable)	Mediolateral (ML; i.e., side-to-side) optical flow perturbations applied during treadmill walking using a projection-based virtual reality system.
Study Design	A randomized, crossover design that included a control session of normal unperturbed walking and an experimental session that incorporated mediolateral optical flow perturbations during walking.
Subject Population	Inclusion Criteria
key criteria for Inclusion and Exclusion:	
 1. Subjects Age 65+ years 2. Be able to walk without an assistive aid (i.e., walker, cane) 3. Have the full capacity to provide informed consent
	Exclusion Criteria

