2 STUDY OBJECTIVE

The purpose of this proof-of-concept study is to evaluate change in walking balance in older adults responding to a single session of optical flow perturbation training compared to a control session of normal walking.

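### Should the perturbation-versus-normal-walking contrast be adjusted for the Pre values rather than rest on the planned change-score interaction?

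*Combined protocol and SAP*

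**What the plan says.** Section 6.1 (Statistical Methods) plans: "A two-way rmANOVA will test for significant main effects and interactions between time (Pre versus Post) and experimental session (perturbations versus normal walking". Section 5 defines efficacy on the same scale: "Efficacy measurements will be made using the change in each outcome measure after walking normally or with optical flow perturbations". Section 4 shows that Pre is measured in each session before that session's walking block: "Subjects will then complete a block protocol design with pre and post measurements separated by up to 20 min of normal treadmill walking", or the same length of walking with perturbations. No section uses Pre as a covariate.

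The contrast at issue is the secondary objective in Section 2.2, "Contrast effects of walking with optical flow perturbations to those of normal treadmill walking". It also appears in Section 2 as "optical flow perturbation training compared to a control session of normal walking".

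Two features of the design bear on the choice of analysis. Section 3.1 says of washout "These walking trials will last up to 20 min and will be separated by at least one week", and of sequence allocation only "assigned at enrollment using a random number generator". The synopsis states that the study looks for "the presence of aftereffects in older adults following a single session of optical flow perturbation training".

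**The concern.** The time-by-session interaction is the only planned comparison that separates the effect of the perturbations from the effect of time on the treadmill, and Section 3.2 caps enrolment at 20. A change-score contrast subtracts the whole Pre difference between sessions, so it fixes the slope on that difference at 1. If Pre and Post are only moderately correlated on the session-difference scale, a slope of 1 subtracts too much and adds noise. Estimating the slope from Pre values already in hand would need no new data or visits, and the contrast could then be estimated more precisely at no cost beyond a few words in the SAP.

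**Working it through.** **The plan's own figure.** Section 6 gives 14 per group for 90% power, from 1.38 (SD 0.20) against 1.20 (SD 0.10). The pooled SD is √((0.20² + 0.10²)/2) = 0.158 and the standardised difference is 0.18/0.158 = 1.138. A t test with 14 per group has power 0.901 one-sided and 0.826 two-sided, so the figure reproduces as a one-sided calculation. It compares older with young adults and therefore supplies no within-person SD or correlation for the crossover contrast. Everything below about c, the variance ratio and carry-over is assumed.

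**Set-up.** Let D_pre = B Pre − A Pre, D_post = B Post − A Post, c = their correlation, k = SD(D_post)/SD(D_pre), and n1, n2 = numbers in the two sequences. The planned interaction is the mean of D_post − D_pre. The alternative regresses D_post on the uncentred D_pre plus a sequence term coded ±1/2 and reads off the intercept.

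**Variance ratio, adjusted to planned:**

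k²(1 − c²)/(1 + k² − 2kc) × (n − 3)/(n − 4) × n(1/n1 + 1/n2)/4

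With k = 1 and equal sequences this is (1 + c)/2 × (n − 3)/(n − 4). For c = 0.5: 0.75 × 17/16 = 0.797 at n = 20, and 0.75 × 11/10 = 0.825 at n = 14.

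Section 3.1 mentions no blocking, so the last factor should be averaged over simple randomisation (at least 2 per sequence). That average is 1.060 at n = 20 and 1.090 at n = 14.

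| | c = 0.4 | c = 0.5 | c = 0.75 | Break-even c |
|---|---|---|---|---|
| n = 20, balanced | 0.744 | 0.797 | 0.930 | 0.88 |
| n = 20, simple randomisation | 0.788 | 0.844 | 0.985 | 0.78 |
| n = 14, balanced | 0.770 | 0.825 | 0.963 | 0.82 |
| n = 14, simple randomisation | 0.839 | 0.899 | 1.049 | 0.67 |

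The break-even values are for variance. The adjusted analysis also gives up two degrees of freedom (17 against 19, or 11 against 13), which lowers the break-even for interval width a little further.

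**Power** for an effect that the planned test detects with 80% power, simulated under simple randomisation with k = 1 and no carry-over, at c = 0.4/0.5/0.75: about 88/86/80% at n = 20; about 85%, 83 to 84% and 77% at n = 14.

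**Dropping the sequence term.** The factor becomes (n − 2)/(n − 3) and the split no longer matters. At c = 0.4/0.5 the ratios are 0.70 × 18/17 = 0.741 and 0.75 × 18/17 = 0.794 at n = 20, and 0.70 × 12/11 = 0.764 and 0.75 × 12/11 = 0.818 at n = 14. But a period effect then biases the estimate whenever the sequences are unequal. A split differing by 4 or more has probability 0.50 at n = 20 and 0.42 at n = 14.

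**Unequal variances.** At c = 0.5 and k = 1.25, the leading term is 1.5625 × 0.75/(1 + 1.5625 − 1.25) = 0.893. Under simple randomisation the ratio is 0.893 × 1.0625 × 1.060 = 1.01 at n = 20 and 0.893 × 1.1 × 1.090 = 1.07 at n = 14. A Post SD 25% larger therefore removes the gain.

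**Carry-over.** Suppose Session B leaves a shift L in both Pre and Post of a later Session A. In that sequence D_pre and D_post both move by −L, so averaged over the two sequences both move by −L/2. The planned contrast cancels this: −L/2 − (−L/2) = 0. The adjusted one does not: −L/2 − c(−L/2) = −(1 − c)L/2. With L = 0.5 SD of the session difference, the bias is −0.175, −0.125 and −0.075 at c = 0.3, 0.5 and 0.7. With balanced sequences and no true session effect, simulated Type I error at those values is about 5% for the planned test throughout. For the adjusted test it is 11/9/7% at n = 20 and 9/7/6% at n = 14.

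**The case for a change.** The case for adjusting is sound as algebra. The interaction is exactly a change-score contrast, the Pre values cost nothing more to use, and without carry-over the adjusted test keeps its 5% level even with a 9/5 split or k = 1.25. In a sample this small, a variance reduction of 16 to 21% at moderate c is worth having, and reporting both analyses would show readers whether the answer depends on the choice. All of that stands.

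What does not stand is the step from a possible gain to a needed change. The gain requires moderate c, similar Pre and Post variances and negligible carry-over, and the documents settle none of these. Modest departures combine to remove it. Carry-over is also not a remote worry here: persistence of the training effect is what the study is looking for, and the change score is the analysis that removes a persistent shift common to Pre and Post. Reporting two analyses of each of six outcomes would also add analytic choice to a proof-of-concept study.

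A separate matter is that the synopsis describes a one-way analysis of time within each session. It does not alter this point, because Section 6.1 states the analysis that addresses the between-session contrast.

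**Conclusion.** No change to the plan follows. The time-by-session interaction is a valid test of the secondary-objective contrast, agrees with Section 5's definition of efficacy as change, and is unaffected by any carry-over that shifts Pre and Post equally. With a sequence term, adjustment under simple randomisation would lower variance by about 16 to 21% with 20 people, or 10 to 16% with 14, if c is 0.4 to 0.5, variances are equal and carry-over is absent. By c = 0.75 the gain is 1.5% with 20 people and has become a 5% loss with 14. The price is a bias of size (1 − c)L/2 under shared carry-over L. At L = 0.5 SD that means a Type I error of about 7 to 11% with 20 people and 6 to 9% with 14, for c from 0.7 down to 0.3. Since c, the variance ratio and L are all assumptions, a statistician could reasonably prefer either analysis. An analyst who wants the adjusted estimate can report it as secondary, with the planned interaction kept primary. The within-session Pre-to-Post analysis for the primary objective in Section 2.1 is not touched.

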6 STATISTICAL CONSIDERATION

Sample size is based on our published estimates of age-related differences in balance outcome measures. n=14 subjects per group would have 90% power to detect ($p<0.05$) a difference in dynamic instability during visually perturbed walking between healthy older (1.38 ± 0.20 , unitless) and healthy young (1.20 ± 0.10 , unitless) adults (Franz et al., 2015). This number of subjects would also sufficiently power our detecting differences in step width variability (8.92 ± 1.00 vs. 4.02 ± 0.96) (Francis et al., 2015).

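### Three primary outcomes are tested at an unadjusted 0.05 with no success rule; if any one counts as positive, the chance of a false positive is up to 14%

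*Combined protocol and SAP*

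**What the plan says.** The synopsis, under Efficacy Evaluations, lists three primary outcome measures: "1) Change in Postural Sway", "2) Change in kinematic (step width) variability" and "3) Change in foot placement targeting accuracy". Three secondary outcomes follow.

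The analysis is described in two places, and the descriptions differ:

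- **Synopsis, Statistical Analysis Plan:** "A one-way, repeated-measures analysis of variance will test for effects of time on dependent variables collected from each session". The threshold is "Significance will be defined using an alpha level of 0.05".
- **Section 6.1:** "A two-way rmANOVA will test for significant main effects and interactions between time (Pre versus Post) and experimental session (perturbations versus normal walking"). The threshold is "Significance will be defined for each main effect using an alpha level of 0.05". That sentence covers main effects and gives no alpha for the interaction.

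Section 6 bases the sample size on a p<0.05 criterion ("n=14 subjects per group would have 90% power to detect") with no allowance for several primary outcomes. Nowhere do the documents adjust for multiple outcomes, order the tests, pick a lead outcome, require all three to be significant, or say which effect in the model decides the result.

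**The concern.** With three outcomes of equal rank and no success rule, the plan leaves open what counts as a positive study. If none of the outcomes truly changes, three separate tests give three chances of a significant result. Nothing in the text stops one such result from being reported as evidence that perturbation training changes walking balance. The error rate behind that claim would then exceed the 0.05 attached to each test.

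The choice of effect adds to the ambiguity. Section 2 states the purpose as a comparison of perturbation training with a session of normal walking, and section 2.2 repeats that contrast as the secondary objective. In the two-way model this comparison is the time-by-session interaction, the one effect for which section 6.1 gives no alpha. The synopsis analysis looks at time within each session and does not make the comparison at all.

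**Working it through.** **Inputs.** Three primary outcomes (synopsis); 0.05 per test (synopsis and section 6.1); n=14 (section 6) and a maximum of 20 (section 3.2). The documents give no correlations between outcomes, so these are assumed and varied.

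**The plan's own figure.** The documents state no family-wise error rate. The only related figure is 14 per group for 90% power. From section 6, the difference is 1.38 − 1.20 = 0.18, the pooled SD is √((0.20² + 0.10²)/2) = 0.158, and d = 0.18/0.158 = 1.14. A two-sample t test with n=14 per group has 90.1% power one-sided at 0.05 and 82.6% two-sided. The figure therefore reproduces one-sided, for a single outcome.

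**Family-wise error, one test per outcome, independent outcomes, no true effects.**
1 − (1 − 0.05)³ = 1 − 0.8574 = 0.1426, or 14.3%.

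**Correlated outcomes.** Three two-sided tests at 0.05 with a common correlation ρ, simulated with no true effects (4 million draws, normal):

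| Assumed ρ | Chance of at least one false positive |
|---|---|
| 0 | 14.3% |
| 0.3 | 13.6% |
| 0.5 | 12.5% |
| 0.7 | 10.9% |
| 0.8 | 9.8% |
| 0.9 | 8.4% |

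Repeating this with t tests on n−1 degrees of freedom (200,000 draws each), the form that the interaction test takes in a 2×2 within-subject design, gives nearly the same values: at ρ=0.7, 11.1% with n=14 and 11.2% with n=20.

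**After adjustment.** Holm compares the smallest p-value with 0.05/3 = 0.0167, the next with 0.05/2 = 0.025 and the last with 0.05. With no true effects, the error is decided at the first step: 1 − (1 − 0.0167)³ = 4.9% if independent, and at most 5% under any correlation.

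**Power cost.** The smallest standardised paired effect detectable with 80% power, two-sided, from the noncentral t:

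| n | At 0.05 | At 0.0167 (strictest Holm step) |
|---|---|---|
| 20 | 0.66 SD | 0.78 SD |
| 14 | 0.81 SD | 0.97 SD |

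**The case against.** **The plan makes no family-wise promise.** A reader might infer that it claims a 5% error rate across its primary outcomes and breaks that claim. It does not. Both passages give a per-test level, and each test holds that level. The inflation depends on a reading, that any one success suffices, which the plan neither states nor excludes. This objection stands, and the point is limited to that reading. If all three outcomes had to be significant, there would be no inflation, but the plan does not say that either.

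**How many tests count.** A reader might also count every F test in the two-way model for each outcome and arrive at a much higher error rate. The documents do not support that count. Section 6.1 sets an alpha for main effects only, so the interaction has none. The primary outcomes are changes, and the session main effect averages over pre and post, so it does not test change. The figures here use one test per outcome.

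**The correlations are unknown.** Sway and step width variability come from the same motion-capture recordings (section 5), so a high correlation between them cannot be excluded. This is fair. It lowers the figure, but even at 0.9 the rate is about 8%, still above 5%.

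**It is a proof-of-concept study.** It covers one training session and at most 20 people, and its primary objective is to quantify change. Unadjusted estimates with confidence intervals, openly labelled as such, could be defended. This reduces the severity. It does not remove the need for text, because the plan ranks outcomes as primary and secondary, sets a significance threshold and cites a power calculation.

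**Conclusion.** The concern holds in a limited form. Three primary outcomes are tested at an unadjusted 0.05, and the plan has no rule for what makes the study positive. If any one significant primary outcome is taken as a positive result, the chance of at least one false positive is up to 14% when nothing has changed. The value depends on the correlation between outcomes, which the documents do not give. All the figures assume one two-sided test per outcome, a common correlation and no true effect on any outcome.

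The severity is modest, given the proof-of-concept purpose. It is worth correcting because the remedy is cheap and also resolves the question of which test decides the result.

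**What to change.** Change the synopsis and section 6.1 together.

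1. **Reconcile the analyses.** State one model in both places. The one-way test per session and the two-way model cannot both be the primary analysis, and a multiplicity rule cannot be applied until this is settled.
2. **Name the decisive test.** For each primary outcome, make it the time-by-session interaction, which contrasts perturbation with normal walking, and give it an explicit two-sided alpha.
3. **Control the error across outcomes.** Apply Holm to the three interaction tests at a family-wise 0.05 (0.0167, then 0.025, then 0.05). Alternatively, name one primary outcome, test it at 0.05 and move the other two to secondary. The two options are not equivalent: the second supports a narrower claim about a single outcome.
4. **Label the rest.** Report the remaining effects and all secondary outcomes with 95% confidence intervals, as exploratory.

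No procedure, visit or enrolment number needs to change. Holm does cost power: at its strictest step the detectable paired effect rises from 0.66 to 0.78 SD at n=20 and from 0.81 to 0.97 SD at n=14. Section 6, which uses p<0.05, should acknowledge this. Naming a single primary outcome costs no power for that outcome.
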